### Endpoints

**Primary:** patient pain/anxiety score as indicated by survey, and quantity of Lidocaine Hydrochloride (Xylocaine) Injection with Epinephrine

**Secondary:** Blood pressure and heart rate, any history of Mohs surgery (any location, any provider)

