### Research Question and Aims

Hypothesis: Supplementing lidocaine/epinephrine injections with intralesional lidocaine jelly will decrease the overall quantity of lidocaine/epinephrine injectable used, and will decrease patients' self-reported pain/anxiety associated with needle sticks.

Objectives: To assess how using lidocaine jelly in Mohs surgery impacts 1) the overall quantity of lidocaine/epinephrine injectable needed to maintain anesthesia, and 2) patients' pain/anxiety associated with anesthesia injections.

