### Power Statement:

Power simulations were based on anticipated analysis of group differences via *t*-tests, Chi-square tests, and Wilcoxon rank-sum tests. These simulations suggested that enrollment of 250 total patients (125 each in control/placebo group and lidocaine jelly treatment group) would allow us to detect a moderate effect ( $d = .5$ ,  $w = .3$ , and  $d=.5$  respectively) of differences between groups at a significance level of  $p < .05$  with power of 90% or greater in our planned analyses.

**Data Analysis Plan:** Primary analyses of interest are descriptive statistics for measures of pain, anxiety, biometric indicators (e.g., heart rate, blood pressure), and amount of total lidocaine administered by injection for each group. Secondary analyses will include statistical tests (e.g., *t*-tests,  $\chi^2$ , and Wilcoxon rank-sum) for comparison between control and treatment group for differences on pain, anxiety, and vital signs. Additional analysis of differences in pain/anxiety across repeated rounds of testing within groups will be explored given sufficient data via descriptive statistics, statistical test, and possible mixed models comparing changes over repeated rounds between groups (dependent on rates of patients with multiple-stage Mohs procedures).

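### Two or three primary outcomes are each sized at p < .05 with no error-rate control, while the analysis plan makes the primary analyses descriptive, labels the tests secondary and names no test of injected quantity

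*Combined protocol and SAP*

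**What the plan says.** - **Research Question and Aims.** The hypothesis is directional: the jelly "will decrease the overall quantity of lidocaine/epinephrine injectable used", and will also lower pain and anxiety linked to needle sticks. Quantity and pain/anxiety are numbered as two objectives.
- **Endpoints.** Primary: "patient pain/anxiety score as indicated by survey, and quantity of Lidocaine Hydrochloride (Xylocaine) Injection with Epinephrine". Blood pressure and heart rate are secondary.
- **Power Statement.** The size is "enrollment of 250 total patients (125 each in control/placebo group and lidocaine jelly treatment group"). The claim is that this suffices, "with power of 90% or greater in our planned analyses", to find d = .5, w = .3 and d = .5 by t, chi-square and Wilcoxon tests at p < .05.
- **Data Analysis Plan.** It opens with "Primary analyses of interest are descriptive statistics for measures of pain, anxiety, biometric indicators" and goes on to total injected lidocaine. Tests come under secondary analyses, for pain, anxiety and vital signs. Injected quantity is not in the list of tested outcomes.

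No section ranks the primary outcomes, divides alpha, names a lead endpoint or defines a positive trial. Whether tests are one- or two-sided is not stated.

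**The concern.** The sections disagree about what the primary analysis is. The hypothesis and the sample size call for tests of group differences. The Data Analysis Plan treats the primary analyses as descriptive and leaves one of the named primary endpoints, injected quantity, without a listed test. The same plan puts heart rate and blood pressure among the primary analyses, although the Endpoints section makes them secondary.

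With no decision rule, a result below .05 on any one primary outcome could be reported as showing that the jelly works. An inert jelly would then have more than a 5% chance of such a claim.

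**Working it through.** **Inputs.** From the Power Statement: 125 per arm, d = .5, w = .3, alpha .05 per test, power at least 90%. From the Endpoints section and the Data Analysis Plan: k = 2 outcomes (quantity and one pain/anxiety score) or k = 3 (quantity, pain, anxiety). Assumed, because the documents are silent: two-sided tests, the correlations between outcomes, and, in the base case, everyone evaluable.

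**1. The plan's own power figure.** For the t-test, the noncentrality is d × √(n/2) = 0.5 × √62.5 = 3.953, with 248 degrees of freedom.

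| Test | Power at alpha .05 |
|---|---|
| t-test, d = .5 | 97.6% |
| Wilcoxon, d = .5 (normal data, relative efficiency 3/π) | 97.0% (97.1% simulated) |
| Chi-square, w = .3, N = 250, 1 df | 99.7% |

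The statement of 90% or greater is reproduced.

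**2. Chance of at least one false positive at .05 each.** Under independence it is 1 − 0.95^k:
- k = 2: 1 − 0.9025 = 9.75%
- k = 3: 1 − 0.857375 = 14.3%

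With correlated test statistics (simulated, 1,000,000 draws):

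| Assumed common correlation | k = 2 | k = 3 |
|---|---|---|
| 0 (exact) | 9.75% | 14.3% |
| 0.5 | 9.1% | 12.5% |
| 0.7 | 8.3% | 10.9% |
| 0.9 | 7.1% | 8.4% |

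Pain and anxiety come from one survey and are probably correlated. If only those two are correlated, at 0.5 to 0.7, and quantity is independent, k = 3 gives 13.7% to 12.9%. The range is about 7–14%, and every case exceeds 5%.

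**3. Power under Holm.** The strictest step for three tests is .05/3 = .0167. With d = .5 and 125 evaluable per arm:
- t-test: 93.8%, a loss of 97.6 − 93.8 = 3.8 points
- Wilcoxon, normal data: 92.6% by relative efficiency, 91.9% by simulation, so a loss of 4.4 to 5.2 points
- chi-square, 1 df: 99.1%

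**4. Sensitivity to evaluable numbers** (t-test, d = .5, alpha .0167):

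| Evaluable per arm | Power |
|---|---|
| 125 | 93.8% |
| 112 | 90.7% |
| 106 | 88.9% |
| 100 | 86.8% |

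The smallest number holding 90% is about 110 per arm for the t-test, a loss of 1 − 110/125 = 12%, and about 115 for the Wilcoxon. At the worst-case Wilcoxon efficiency of 0.864, power with 125 per arm is 89.5%.

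**5. Why evaluable numbers matter here.** Under Methods, the first two surveys precede the first stage, the jelly or lubricant goes on after that stage, and later surveys are given before each subsequent stage. Unless reconstruction counts as a stage, which Methods does not say, a one-stage patient has no pain or anxiety score after the jelly. The multi-stage share is not given. If it were 80% (assumed), 100 per arm would be evaluable and power would be 86.8%. If it were 50%, with about 62 per arm, power would be about 64%.

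**The case against.** The strongest reply is that the plan has no primary hypothesis test. Its primary analyses are descriptive, and descriptive summaries have no type I error. This stands to the extent that the 7–14% applies only if the secondary p-values are used to support primary conclusions. It does not remove the problem. Summaries alone cannot test a directional hypothesis in a randomized, placebo-controlled trial, and the 250 patients are justified entirely by tests at p < .05.

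A second reply is that the wording of the hypothesis, which joins its two parts, could require success on both, and then no correction is needed. No section states that rule, and the objectives are numbered separately.

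Three stronger readings are tempting but unsupported:
- A reader might infer that the error rate is more than double the nominal 5%. On the two-outcome reading the independent figure is 9.75%, already below double, and correlation lowers it. The third outcome depends on scoring pain and anxiety separately, and a test of quantity is implied by the hypothesis and the sizing, not listed.
- A reader might count everything listed under the primary analyses, heart rate and blood pressure included, and arrive at a much larger rate. That applies a test error rate to summaries the plan calls descriptive, and the Endpoints section makes the vital signs secondary.
- A reader might infer that 250 patients already cover a correction. That holds for d = .5 with nearly all patients evaluable on every outcome. The documents do not establish this, particularly for pain and anxiety in one-stage patients.

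**Conclusion.** The concern holds in a conditional form. The plan has two or three unranked primary outcomes, no error-rate control, and sections that conflict on whether the primary analysis is descriptive or a test. If the p-values carry the stated hypothesis, as the sizing suggests they will, the chance of at least one false primary claim is about 7–14%. The low end is two outcomes correlated at 0.9; the high end is three independent outcomes. The correlations are assumed. The conflict between sections and the missing test of injected quantity need no assumption. The point should be fixed before analysis. It does not show that the trial is too small: with 125 evaluable per arm and d = .5, a correction leaves power above 90% for the t-test, and for the Wilcoxon with near-normal data.

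**What to change.** In Endpoints and the Data Analysis Plan:
1. Name one between-arm test each of injected quantity, pain score and anxiety score as the primary analysis.
2. Name the post-dressing survey at which the pain and anxiety scores are taken, and say how patients without that survey are handled.
3. Apply Holm's procedure to the three tests at an overall two-sided 5%. This holds the family-wise error at or below 5% whatever the correlation.
4. Keep heart rate and blood pressure secondary in both sections, with no confirmatory claim.
5. Restate power at the strictest Holm step (.0167), for d = .5 and 125 evaluable per arm, as about 94% (t-test) or 92–93% (Wilcoxon, near-normal data). Add that the t-test holds 90% down to about 110 evaluable per arm, and that power for pain and anxiety is lower if one-stage patients have no survey after the jelly.

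The alternative is to keep the primary analysis descriptive and say that no confirmatory claim will be made. That is coherent, but it gives up the test of the hypothesis for which the trial was sized.

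The cost is wording in two sections and about 4 percentage points of power at the strictest step. Whether more patients are needed for pain and anxiety depends on the multi-stage share, which the sponsor should state.
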